#### 9. SUBJECT COMPLETION AND WITHDRAWAL

# 9.1. Subject Completion

A patient will be considered complete if the patient receives a minimum of 9 days of dosing with lapatinib and pre-dose and post-dose tumor samples are adequate for analysis of biomarkers.

2. Glucocorticoid daily doses (oral) ≤ 1.5mg of dexamethasone (or equivalent) are allowed. Glucocorticoid conversions are provided in parentheses.

## 9.2. Subject Withdrawal

A patient may voluntarily discontinue participation in the study at any time. The investigator may also at his or her discretion, discontinue the patient from participating in the study at any time. If a patient prematurely discontinues from study, every effort must be made to perform all post study evaluations listed in Section 6.4.

# 10. ADVERSE EVENTS (AE) AND SERIOUS ADVERSE EVENTS (SAE)

The investigator is responsible for the detection and documentation of events meeting the criteria and definition of an AE or SAE as provided in this protocol. During the study, when there is a safety evaluation, the investigator or site staff will be responsible for detecting AEs and SAEs, as detailed in this section of the protocol.

When applicable, AEs and SAEs will be graded using the NCI Common Terminology Criteria for Adverse Events (CTCAE), version 3. A copy of this manual is contained in the Study Reference Manual.

#### 10.1. Definition of an AE

Any untoward medical occurrence in a patient or clinical investigation subject, temporally associated with the use of a medicinal product, whether or not considered related to the medicinal product.

An AE can therefore be any unfavorable and unintended sign (including an abnormal laboratory finding), symptom, or disease (new or exacerbated) temporally associated with the use of a medicinal product.

## Examples of an AE include:

Exacerbation of a chronic or intermittent pre-existing condition including either an increase in frequency and/or intensity of the condition.

New conditions detected or diagnosed after investigational product administration even though it may have been present prior to the start of the study.

Signs, symptoms, or the clinical sequelae of a suspected interaction.

Signs, symptoms, or the clinical sequelae of a suspected overdose of either investigational product or a concurrent medication (overdose per se should not be reported as an AE/SAE).

#### Examples of an AE do not include a/an:

Medical or surgical procedure (e.g., endoscopy, appendectomy); the condition that leads to the procedure is an AE.

Situations where an untoward medical occurrence did not occur (social and/or convenience admission to a hospital).

Anticipated day-to-day fluctuations of pre-existing disease(s) or condition(s) present or detected at the start of the study that do not worsen.

The disease/disorder being studied, or disease progression, signs, or symptoms of the disease/disorder being studied, unless more severe than expected for the subject's condition.

For GSK clinical studies, AEs may include pre- or post-treatment events that occur as a result of protocol-mandated procedures (i.e., invasive procedures, modification of subject's previous therapeutic regimen).

#### 10.2. Definition of a SAE

A serious adverse event is any untoward medical occurrence that, at any dose:

- a. Results in death.
- b. Is life-threatening.

NOTE: The term 'life-threatening' in the definition of 'serious' refers to an event in which the subject was at risk of death at the time of the event. It does not refer to an event, which hypothetically might have caused death, if it were more severe.

c. Requires hospitalization or prolongation of existing hospitalization.

NOTE: In general, hospitalization signifies that the subject has been detained (usually involving at least an overnight stay) at the hospital or emergency ward for observation and/or treatment that would not have been appropriate in the physician's office or out-patient setting. Complications that occur during hospitalization are AEs. If a complication prolongs hospitalization or fulfills any other serious criteria, the event is serious. When in doubt as to whether "hospitalization" occurred or was necessary, the AE should be considered serious.

Hospitalization for elective treatment of a pre-existing condition that did not worsen from baseline is not considered an AE.

d. Results in disability/incapacity, or

NOTE: The term disability means a substantial disruption of a person's ability to conduct normal life functions. This definition is not intended to include experiences of relatively minor medical significance such as uncomplicated headache, nausea, vomiting, diarrhea, influenza, and accidental trauma (e.g. sprained ankle) which may interfere or prevent everyday life functions but do not constitute a substantial disruption.

- e. Is a congenital anomaly/birth defect.
- f. Medical or scientific judgment should be exercised in deciding whether reporting is appropriate in other situations, such as important medical events that may not be immediately life-threatening or result in death or hospitalization but may jeopardize

the subject or may require medical or surgical intervention to prevent one of the other outcomes listed in the above definition. These should also be considered serious. Examples of such events are invasive or malignant cancers, intensive treatment in an emergency room or at home for allergic bronchospasm, blood dyscrasias or convulsions that do not result in hospitalization, or development of drug dependency or drug abuse.

#### Additional protocol defined criteria:

- All grade 4 laboratory abnormalities.
- Cardiovascular events have been seen in patients taking other compounds that inhibit ErbB2 when used in combination with or following anthracyclines and interstitial pneumonitis has been reported in patients taking compounds that inhibit ErbB1. As a precaution, the following will be reported as SAE:
  - Cardiac related events meeting the criteria of a primary cardiac endpoints (which is, CHF and cardiac death) will be reported as serious adverse events (SAEs).

Note: If a secondary cardiac endpoint fulfils any of the criteria for 'seriousness' (e.g. hospitalisation), it must also be reported as an SAE. **Symptomatic** declines in LVEF that do not meet the criteria for a secondary cardiac endpoint are not expected to be common. These events will be reported as AEs or SAEs, if applicable, as described above. **Asymptomatic** declines in LVEF that do not meet the criteria for 'significant,' do not qualify as a secondary cardiac endpoint and will not be reported as AEs.

Any signs or symptoms of pneumonitis that are ≥ Grade 3 (NCI CTCAE, version 3.0) (defined as radiographic changes and requiring oxygen). Refer to [Cancer Therapy Evaluation Program, 2003] CTCAE (version 3.0) grading of pneumonitis/pulmonary infiltrates.

# 10.3. Lack of Efficacy

"Lack of efficacy" per se will not be reported as an AE. The signs and symptoms or "clinical sequelae resulting from lack of efficacy will be reported if they fulfil the AE or SAE definition (including clarifications).

# 10.4. Clinical Laboratory Abnormalities and Other Abnormal Assessments as AEs and SAEs

Abnormal laboratory findings (e.g., clinical chemistry, hematology, urinalysis) or other abnormal assessments (e.g., ECGs, vital signs, etc.) that are judged by the investigator as **clinically significant** will be recorded as AEs or SAEs if they meet the definition of an AE, as defined in Section 10.1 ("Definition of an AE"), or SAE, as defined in Section 10.2 ("Definition of a SAE"). Clinically significant abnormal laboratory findings or other abnormal assessments that are detected during the study or are present at baseline and significantly worsen following the start of the study will be reported as AEs and SAEs. However, clinically significant abnormal laboratory findings or other abnormal

assessments that are associated with the disease being studied, unless judged by the investigator as more severe than expected for the patient's condition, or that are present or detected at the start of the study and do not worsen, will **not** be reported as AEs or SAEs.

The investigator will exercise his or her medical and scientific judgment in deciding whether an abnormal laboratory finding or other abnormal assessment is clinically significant.

# 10.5. Time Period, Frequency, and Method of Detecting AEs and SAEs

Patients will be monitored for the occurrence of AEs/SAEs at each study visit or contact, and at the 28-day post study follow-up visit. The investigator or designee will inquire about AEs by asking the following general questions:

- 1. How are you feeling?
- 2. Have you had any medical problems since your last visit?
- 3. Have you taken any new medications since your last visit?

All AEs and SAEs, regardless of relationship to study medications, will be recorded from study treatment initiation until 72 hours after permanent discontinuation of study treatment. Only AEs and SAEs assessed and related to study medications will be recorded between 72 hours and 28 days after the permanent discontinuation of study treatment.

# 10.6. Recording of AEs and SAEs

When an AE/SAE occurs, it is the responsibility of the investigator to review all documentation (e.g., hospital progress notes, laboratory, and diagnostics reports) relative to the event. The investigator will then record all relevant information regarding an AE/SAE on the CRF. It is not acceptable for the investigator to send photocopies of the subject's medical records to GSK in lieu of completion of the appropriate AE/SAE CRF pages. However, there may be instances when copies of medical records for certain cases are requested by GSK. In this instance, all subject identifiers will be blinded on the copies of the medical records prior to submission to GSK.

The investigator will attempt to establish a diagnosis of the event based on signs, symptoms, and/or other clinical information. In such cases, the diagnosis should be documented as the AE/SAE and not the individual signs/symptoms.

## 10.7. Evaluating AEs and SAEs

#### 10.7.1. Assessment of Intensity

The investigator will make an assessment of intensity for each AE and SAE reported during the study. The assessment will be based on the investigator's clinical judgment and using the Cancer Evaluation Program, Common Terminology Criteria for Adverse Events(CTCAE), Version 3, when appropriate. For non-CTCAE graded events, the intensity of each AE and SAE recorded in the CRF should be assigned to one of the following categories:

Mild: An event that is easily tolerated by the subject, causing minimal discomfort and not interfering with everyday activities.

Moderate: An event that is sufficiently discomforting to interfere with normal everyday activities.

Severe: An event that prevents normal everyday activities.

An AE that is assessed as severe should not be confused with a SAE. Severity is a category utilized for rating the intensity of an event; and both AEs and SAEs can be assessed as severe. An event is defined as 'serious' when it meets one of the pre-defined outcomes as described in Section 10.2, "Definition of a SAE".

## 10.7.2. Assessment of Causality

The investigator is obligated to assess the relationship between investigational product and the occurrence of each AE/SAE. The investigator will use clinical judgment to determine the relationship. Alternative causes, such as natural history of the underlying diseases, concomitant therapy, other risk factors, and the temporal relationship of the event to the investigational product will be considered and investigated. The investigator will also consult the CIB/IB and/or Product Information, for marketed products, in the determination of his/her assessment.

There may be situations when an SAE has occurred and the investigator has minimal information to include in the initial report to GSK. However, it is very important that the investigator always make an assessment of causality for every event prior to transmission of the SAE CRF to GSK. The investigator may change his/her opinion of causality in light of follow-up information, amending the SAE CRF accordingly. The causality assessment is one of the criteria used when determining regulatory reporting requirements.

The investigator will provide the assessment of causality as per instructions on the SAE form in the CRF.

## 10.8. Follow-Up of AEs and SAEs

After the initial AE/SAE report, the investigator is required to proactively follow each subject and provide further information to GSK on the subject's condition.

All AEs and SAEs documented at a previous visit/contact and are designated as ongoing, will be reviewed at subsequent visits/contacts.

All AEs and SAEs will be followed until resolution, until the condition stabilizes, until the event is otherwise explained, or until the subject is lost to follow-up. Once resolved, the appropriate AE/SAE CRF page(s) will be updated. The investigator will ensure that follow-up includes any supplemental investigations as may be indicated to elucidate the nature and/or causality of the AE or SAE. This may include additional laboratory tests or investigations, histopathological examinations, or consultation with other health care professionals.

GSK may request that the investigator perform or arrange for the conduct of supplemental measurements and/or evaluations to elucidate as fully as possible the nature and/or causality of the AE or SAE. The investigator is obligated to assist. If a subject dies during participation in the study or during a recognized follow-up period, GSK will be provided with a copy of any post-mortem findings, including histopathology.

New or updated information will be recorded on the originally completed "SAE" CRF, with all changes signed and dated by the investigator. The updated SAE CRF should be resent to GSK within the time frames outlined in Section 10.9.

# 10.9. Prompt Reporting of SAEs to GSK

SAEs will be reported promptly to GSK as described in the following table once the investigator determines that the event meets the protocol definition of an SAE.

| 10.9.1. | Timeframes for | Submitting | SAE Re | ports to GSK |
|---------|----------------|------------|--------|--------------|
|         |                |            |        |              |

|             | Initial SAE Reports |                    | Follow-up Information on a
Previously Reported SAE |                            |
|-------------|---------------------|--------------------|---|----------------------------|
| Type of SAE | Time Frame          | Documents          | Time Frame  | Documents                  |
| All SAEs    | 24 hrs              | "SAE" CRF
pages | 24 hrs  | Updated "SAE"
CRF pages |

# 10.9.2. Completion and Transmission of the SAE Reports

Once an investigator becomes aware that an SAE has occurred in a study subject, she/he will report the information to GSK within 24 hours as outlined in Section 10.9, "Prompt Reporting of SAEs to GSK". The SAE CRF will always be completed as thoroughly as possible with all available details of the event, signed by the investigator (or designee), and forwarded to GSK within the designated time frames. If the investigator does not have all information regarding an SAE, he/she will not wait to receive additional

information before notifying GSK of the event and completing the form. The form will be updated when additional information is received.

The investigator will always provide an assessment of causality at the time of the initial report as described in Section 10.7.2, "Assessment of Causality".

Facsimile transmission of the "SAE" CRF is the preferred method to transmit this information to the project contact for SAE receipt. In rare circumstances and in the absence of facsimile equipment, notification by telephone is acceptable, with a copy of the "SAE" CRF sent by overnight mail. Initial notification via the telephone does not replace the need for the investigator to complete and sign the SAE CRF within the time frames outlined in Section 10.9, "Prompt Reporting of SAEs to GSK".

GSK will provide a list of project contacts for SAE receipt, fax numbers, telephone numbers, and mailing addresses.

The following pages of the CRF must accompany the SAE forms that are forwarded to GSK: "Demography", "Medical History", "Concomitant Medications", "Study Medication Records", and "Form D" (if applicable).

## 10.10. Regulatory Reporting Requirements for SAEs

The investigator will promptly report all SAEs to GSK in accordance with the procedures detailed in Section 10.9, "Prompt Reporting of SAEs to GSK." GSK has a legal responsibility to notify, as appropriate, both the local regulatory authority and other regulatory agencies about the safety of a product under clinical investigation. Prompt notification of SAEs by the investigator to the appropriate project contact for SAE receipt is essential so that legal obligations and ethical responsibilities towards the safety of other subjects are met.

The investigator, or responsible person according to local requirements, will comply with the applicable local regulatory requirements related to the reporting of SAEs to regulatory authorities and the Institutional Review Board (IRB)/Independent Ethics Committee (IEC).

This protocol has been filed under an Investigational New Drug (IND) application with the US Food and Drug Administration (FDA). A given SAE may qualify as an IND Safety Report if the SAE is both attributable to the investigational product and unexpected. In this case, all investigators filed to the IND (and associated INDs for the same compound) will receive an Expedited Investigator Safety Report (EISR), identical in content to the IND Safety Report submitted to the FDA.

Expedited Investigator Safety Reports (EISR) are prepared according to GSK policy and are forwarded to investigators as necessary. An EISR is prepared for a SAE that is both attributable to investigational product and unexpected. The purpose of the EISR is to fulfill specific regulatory and Good Clinical Practice (GCP) requirements, regarding the product under investigation.

An investigator who receives an EISR describing a SAE or other specific safety information from GSK will file it with the Investigator Brochure and will notify the IRB or IEC, if appropriate according to local requirements.

## 10.11. Post-study AEs and SAEs

A post-study AE/SAE is defined as any event that occurs outside of the AE/SAE detection period defined in Section 10.5, "Time Period, Frequency, and Method of Detecting AEs and SAEs", of the protocol.

Investigators are not obligated to actively seek AEs or SAEs in former study participants. However, if the investigator learns of any SAE, including a death, at any time after a subject has been discharged from the study, and he/she considers the event reasonably related to the investigational product, the investigator will promptly notify GSK.

# 10.12. SAEs Related to Study Participation

An SAE considered related to study participation (e.g., procedures, invasive tests, a change in existing therapy), even if it occurs during the pre- or post-treatment period, will be reported promptly to GSK (see Section 10.9, "Prompt Reporting of SAEs to GSK").

#### 11. DATA ANALYSIS AND STATISTICAL CONSIDERATIONS

# 11.1. Hypotheses

No formal hypotheses are being tested. The study will focus on obtaining point estimates and 90% confidence intervals of biomarker differences derived from the pre-to-post tumor tissue.

# 11.2. Sample Size Considerations

Twenty evaluable subjects are needed for biomarker analyses.

# 11.2.1. Sample Size Assumptions

In preliminary analysis of the tumor biomarkers in the phase I clinical study EGF10004, the standard deviation of the pre-dose to post-dose percent change in individual biomarkers ranged from 17% to over 600% across multiple dose levels of lapatinib. Although the variability of tumor biomarkers measured in a more homgenous population (i.e. all breast cancer) may be reduced, it is not practical to frame this study as confirmatory hypothesis testing. Thus, results from this study should be viewed as exploratory data analysis, and proposed sample sizes are based on logistic feasibility.

## 11.3. Analysis Populations

All subjects who receive at least one dose of lapatinib will be included in the safety population. All patients for whom valid lapatinib pharmacokinetic concentrations can be estimated will be included in the pharmacokinetic population. All patients who receive at least 9 days of treatment and for whom pre- and post-dose biomarker values have been obtained will be included in the pharmacodynamic population.

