### 5. STUDY POPULATION

Female patients 18 years or older who are amenable to treatment with oral lapatinib and who will receive adjuvant chemotherapy, hormonal therapy or radiation therapy will be enrolled. An evaluable patient must meet all inclusion and exclusion criteria as detailed in Section 5.2 including taking all study medication. In addition, patients must have predose and post-dose tumor tissue samples adequate for biomarker analysis. A GSK medical monitor must approve any deviation from these criteria.

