# 5.1. Number of Subjects

A sufficient number of patients will be enrolled to obtain approximately 20 evaluable patients approximately 16 study centers. Evaluable subjects are defined as those subjects whose pre-treatment tumors are determined by a central laboratory to be ErbB2 positive, which is defined as either IHC 3+ or FISH amplified. Patients must have pre-dose and post-dose tumor tissue samples adequate for biomarker analyses, and have completed lapatinib treatment for a minimum of 9 days. In addition, the elapsed time between last lapatinib dose and surgical resection must be within 24 hours.

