# 7.4. Treatment Assignment

All patients will receive 1500 mg of lapatinib daily. Any patient not completing all required assessments will be replaced.

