#### 11.4.1. Withdrawal

Patients that drop out will be replaced until 20 subjects have been determined to be evaluable.

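### The pharmacodynamic population in Section 11.3 omits two conditions that Section 5.1 sets for an evaluable subject, and no section says which set carries the primary biomarker analysis

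*Supplement*

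**What the plan says.** Section 5.1 sets four conditions for an evaluable subject. The first is central confirmation: "Evaluable subjects are defined as those subjects whose pre-treatment tumors are determined by a central laboratory to be ErbB2 positive". The second and third are adequate pre- and post-dose tissue and at least 9 days of lapatinib. The fourth is timing: "the elapsed time between last lapatinib dose and surgical resection must be within 24 hours".

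Section 11.2 ties the target number to that term: "Twenty evaluable subjects are needed for biomarker analyses". Section 11.4.1 continues enrolment accordingly: "Patients that drop out will be replaced until 20 subjects have been determined to be evaluable".

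Section 11.3 then defines the pharmacodynamic population without using the term: "All patients who receive at least 9 days of treatment and for whom pre- and post-dose biomarker values have been obtained will be included". Section 11.6.2, which describes the analysis of covariance of the tumor markers, names no population.

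Section 5 has its own description of an evaluable patient: "An evaluable patient must meet all inclusion and exclusion criteria as detailed in Section 5.2 including taking all study medication". It also asks for adequate paired tissue and requires medical-monitor approval of deviations. Section 7.4 has a separate replacement rule: "Any patient not completing all required assessments will be replaced".

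**The concern.** The primary endpoint is the pre-to-post comparison of tumor biomarkers, so the set of patients in that comparison determines what the trial estimates. The set that counts toward 20 and the set that Section 11.3 defines are different.

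The patients in the gap can occur by design. Entry rests on the local laboratory's ErbB2 result (Section 5.2.1), and Appendix 1, footnote a, requires only the local result before Day 1 dosing. A patient whom the central laboratory does not confirm can therefore be treated, resected and have paired values. A resection later than 24 hours leads only to contact with the medical monitor (Section 6.7.1). Nothing shown in Section 11 says how either kind of patient is handled.

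At stake is the meaning of the estimates. The study tests no hypothesis, so point estimates and 90% confidence intervals are its main output, and Section 1.5 says they will guide later trials. Mixing in tumors that are not centrally ErbB2 positive, or samples taken outside the planned window, would probably pull the estimates toward no change.

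**Working it through.** **The plan's own figure.** The 20 evaluable subjects cannot be reproduced by a formula. Section 11.2.1 bases the number on logistic feasibility and gives no alpha, power or effect size. The check is therefore a comparison of criteria, followed by an illustration of size.

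**Step 1: criteria side by side.**

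| Condition | 5.1, evaluable | 5, evaluable | 11.3, PD population |
|---|---|---|---|
| Central ErbB2 positive | yes | not stated | not stated |
| At least 9 days of lapatinib | yes | not stated | yes |
| Paired tissue or values | yes | yes | yes |
| Resection within 24 h of last dose | yes | not stated | not stated |
| All eligibility criteria met | not stated | yes | not stated |
| All study medication taken | not stated | yes | not stated |

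Two of the four conditions in Section 5.1 reach Section 11.3 and two do not. A patient treated for more than 9 days who missed one dose can meet Section 5.1 and fail Section 5.

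**Step 2: how many extra patients.** Let f be the share of the Section 11.3 set that fails central positivity or the 24-hour window. The documents give no value, so f is an assumption. The set needed to hold 20 evaluable patients is 20/(1 − f), rounded up:

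- f = 10%: 20/0.90 = 22.2, so 23 (3 extra)
- f = 20%: 20/0.80 = 25 (5 extra)
- f = 30%: 20/0.70 = 28.6, so 29 (9 extra)

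**Step 3: dilution on the ratio scale.** Assume a geometric mean post/pre ratio of 0.50 in evaluable patients and r in the others. The expected estimate is exp[(1 − f)·ln 0.50 + f·ln r].

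| f | r = 1.0 (no change) | r = 0.75 |
|---|---|---|
| 10% | 0.54 | 0.52 |
| 20% | 0.57 | 0.54 |
| 30% | 0.62 | 0.56 |

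**Step 4: against the noise.** Section 11.2.1 gives a standard deviation of percent change from 17% to over 600%. The 90% half-width at n = 20 is t(0.95; 19)·SD/√20, with t = 1.729:

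- SD 17%: 1.729 × 17/4.472 = 6.6 points
- SD 600%: 1.729 × 600/4.472 = 232 points

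On the percent-change scale, if evaluable patients average −50% and the others 0%, the mean shifts by 50f, which is 5, 10 or 15 points at f = 10%, 20% or 30%. That is of the same order as the interval for the least variable markers and negligible for the most variable.

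**The case against.** The strongest reply is that the protocol never calls the Section 11.3 set primary. Section 11.6.2 is silent, Section 11.2 points to evaluable subjects, and Section 11.4 leaves complete details to a Reporting and Analysis Plan that is not shown. This stands in part: which set is primary is an inference. It does not remove the conflict, because Sections 11.2 and 11.3 point to different sets and Section 11 does not define the evaluable set as an analysis population. The lack of a sensitivity analysis may fairly be left to the reporting plan and is not counted as a fault.

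It is also sound practice to enroll to a minimum evaluable number and analyze everyone with paired data. A stopping number that differs from the analyzed number is not in itself an error.

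A reader might infer several stronger things that the documents do not support:

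- **Patients are replaced and then analyzed anyway.** Section 11.4.1 literally replaces those who drop out, and Section 7.4 those with incomplete assessments. Neither names centrally negative or late-resection patients. Enrolment simply continues until 20 are evaluable.
- **There are three rival definitions of evaluable.** Only Sections 5 and 5.1 define the term, and they could be read cumulatively. Section 9.1 defines completion and Section 7.4 governs replacement.
- **Inclusion can be chosen after results are seen.** The literal wording of Section 11.3 fixes inclusion. The two omitted conditions are a laboratory result and an elapsed time, not discretionary calls.
- **Late samples are off drug.** Section 1.4 reports a Day 8 half-life of 9 hours in healthy volunteers at low doses. On that figure, plasma at 28 hours is still 2^(−4/9), about 73%, of the 24-hour level. Section 7.3 adds that xenograft tumor concentrations exceed and lag behind plasma.
- **Centrally negative tumors show no effect.** Lapatinib also inhibits ErbB1, which Section 2.1 includes in the primary objective. A ratio of 1.0 in these patients is a worst case for dilution toward no change.

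**Conclusion.** The conflict is real and sits in the current text. Section 11.3 omits central ErbB2 positivity and the 24-hour window, Section 11.2 says the biomarker analyses need evaluable subjects, and Section 11.6.2 does not decide between them. Sections 5 and 5.1 also disagree on complete medication intake.

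Dilution is the likely direction. The size rests on an assumed true ratio of 0.50, an assumed failing share of 10% to 30%, and an assumed ratio of 0.75 to 1.0 in the patients who fail. Across those assumptions the expected estimate lies between about 0.52 and 0.62. The real shares could be smaller or larger. The shift could matter for low-variance markers and would not be visible for high-variance ones.

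This should be fixed, but it is not critical. The study is phase I, single-arm and exploratory. No error rate, power claim or decision rule depends on the set, so the harm is to the estimates and their interpretation.

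**What to change.** - In Sections 11.3 and 11.6.2, name the Section 5.1 evaluable set as the population for the primary biomarker analysis.
- State that evaluability is determined before the pre-to-post biomarker results are opened. The central ErbB2 status needed for that decision comes from the pre-treatment tissue.
- Keep the present Section 11.3 set, all patients with at least 9 days and paired values, as a named sensitivity analysis.
- Reconcile Sections 5 and 5.1 into one definition of evaluable that says explicitly whether complete medication intake is part of it, and align the replacement rule in Section 7.4 with that definition.

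The cost is wording in five sections and one extra table. The primary set would be slightly smaller than under the present Section 11.3, but it would hold the 20 patients the plan says it needs.
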